#### e10.5.11 Serial DAT Scan Substudy

The primary aim of the serial DAT scan substudy is to determine whether serum urate elevation via oral inosine slows the loss of striatal dopamine transporter (DAT) over two years in early PD as measured by a reduction in DAT radioligand uptake on serial SPECT brain scans. In pursuit of secondary aims, we will determine whether and to what extent change in DAT loss correlates with change in smartphone metrics of PD progression as measured in the 'Smart4SURE' substudy, and will test whether genetic determinants of PD progression (e.g., variants of *SNCA* or *SLC2A*9) or of urate-DAT interaction (e.g., *INPP5K* variants) identify PD subpopulations in whom inosine alters the DAT loss in SURE-PD3.

Quantitative estimates of striatal binding ratios in the left and right hemispheres of the caudate and putamen will be averaged, log-transformed, and modeled in a shared-baseline, repeated measures ANOVA with fixed terms for visit (2 levels), post-baseline x treatment interaction (1 term), gender, gender x visit interaction, MAO-B inhibitor, MAO-B inhibitor x visit interaction, and unstructured covariance between each participant's serial assessments. Back-transformed linear functions of the fixed terms will yield estimates of treatment-group specific percent change over 2 years and will be used to test for treatment-dependent differences in 2-year change in DAT ligand uptake. This model construction increases efficiency by adjusting for baseline, controls for any chance differences in DAT uptake at baseline between treatments, and allows inclusion of all participants in the analysis even if some are lost to follow-up. Both mITT and AT samples will be analyzed, with the mITT results considered primary. Associations between 2-year changes in mean striatal binding ratios and functional measures (e.g., MDS-UPDRS) will be estimated overall from simple correlations and separately by gender and baseline MAO-B inhibitor use. We will test for Simpson's paradox (i.e., incongruence between correlations among- vs. within-groups). Gender-specific and genotype-specific effects will be considered in secondary analyses by including subgroup and subgroup x treatment x post-baseline terms.

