## 10.5.3 Subgroup Analyses

The potential for differential benefit from serum urate elevation among subgroups of patients will be tested by including subgroup, subgroup x time, and subgroup x time x treatment interaction terms into the primary random-slopes model. A significant subgroup x time x treatment 3-way interaction in combination with significantly slower progression among members of a subgroup randomized to serum urate elevation vs. members of the same subgroup randomized to placebo will be taken as evidence of differential benefit. The following subgroups will be considered: sex, race (classified as Asian, Black or African American, Caucasian, or other, including multiracial; or as Caucasian vs. non-Caucasian if fewer than 10% of our sample is non-Caucasian), ethnicity (classified as Hispanic or Latino vs. non-Hispanic), use of MAO-B inhibitors at baseline, and age (both categorized as <65 years vs. ≥65 years and continuous).

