6.6.7 Pharmacogenetics

The above listed and any subsequently designated genetic variants will be tested as potential modifiers of treatment effect. For each genetic variant, the potential for differential benefit from serum urate elevation will be tested by including genotype, genotype x time, and genotype x time x treatment interaction terms into the primary random-slopes model. A significant genotype x time x treatment 3-way interaction in combination with significantly slower progression among members of a genotype randomized to serum urate elevation vs. participants with the same genotype randomized to placebo will be taken as evidence of differential benefit.

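### The DAT substudy's genotype model has no genotype x visit term, so a genotype that only predicts DAT loss can be mistaken for one that modifies the inosine effect

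*Protocol*

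**What the plan says.** Protocol 10.5.11 builds the DAT model on log striatal binding ratio at two visits with a shared baseline. It lists "fixed terms for visit (2 levels), post-baseline x treatment interaction (1 term), gender, gender x visit interaction, MAO-B inhibitor, MAO-B inhibitor x visit interaction", with unstructured covariance between a participant's two scans. For subgroup effects it adds only a subgroup main effect and a subgroup x treatment x post-baseline term: "Gender-specific and genotype-specific effects will be considered in secondary analyses by including subgroup and subgroup x treatment x post-baseline terms".

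The section has a secondary aim for genotype. The substudy "will test whether genetic determinants of PD progression", or of urate-DAT interaction, "identify PD subpopulations in whom inosine alters the DAT loss in SURE-PD3". The examples named are SNCA, SLC2A9 and INPP5K variants.

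Elsewhere the lower-order term is written out. Protocol 10.5.3 tests subgroups on the primary outcome by "including subgroup, subgroup x time, and subgroup x time x treatment interaction terms into the primary random-slopes model", and SAP 6.6.6 does the same. SAP 6.6.7 tests genetic variants by "including genotype, genotype x time, and genotype x time x treatment interaction terms into the primary random-slopes model".

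**The concern.** A test of effect modification has to separate two questions: whether carriers lose DAT faster whatever they are given, and whether inosine changes the loss differently in carriers. The first needs a genotype x visit term and the second needs the three-way term. With only the three-way term present, the model has a single place for a post-baseline genotype difference, and that place is the inosine arm.

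This matters more here than for an arbitrary subgroup, because some of the variants are named as determinants of progression. The property for which they were picked is the one that this model can misread as effect modification. The error is a bias, so it does not shrink as the substudy grows. A larger substudy makes a false finding more likely.

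**Working it through.** The plan states no sample size, power or alpha for this test, so there is no figure to reproduce. The check is of the model algebra, followed by its size under stated assumptions.

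**Inputs.** Model terms are from Protocol 10.5.11. Assumed, because the documents do not give them: 100 or 200 participants with both scans, split 1:1; carrier share p of 20% or 40%; SD of log binding ratio 0.30 at each visit; correlation rho between scans of 0.7 or 0.9. The genotype adds delta = -0.05 log units of change in both arms. There is no treatment effect and no interaction.

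**Step 1: what the model allows.** Let v be the visit effect, t the post-baseline x treatment term and h the three-way term.

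| Group | Change in model | True change |
|---|---|---|
| Placebo, non-carrier | v | v0 |
| Placebo, carrier | v | v0 + delta |
| Inosine, non-carrier | v + t | v0 |
| Inosine, carrier | v + t + h | v0 + delta |

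The two placebo rows must share one value, so v settles near v0 + p x delta. Then t is near -p x delta and h is near delta, although inosine does nothing.

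**Step 2: how much of delta reaches h.** The genotype main effect g takes up a little of it. Take the carrier minus non-carrier difference at each visit in each arm, with equal variances. Both placebo differences estimate g. Their mean has expectation delta/2 and relative variance (1 + rho)/2. The inosine baseline difference also estimates g, with expectation 0 and relative variance 1. Weighting by inverse variance, E(g) = delta/(3 + rho). Since h is the inosine post-baseline difference, adjusted for baseline, less (1 - rho)g:

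E(h) = delta x [1 - (1 - rho)/(3 + rho)]

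The share of delta in h is 86% at rho = 0.5, 92% at 0.7, 95% at 0.8 and 97% at 0.9. Simulation agrees.

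**Step 3: false-positive rate.** Let c = SD^2 / [(n/2) p (1 - p)]. By the same algebra, Var(h) = c(1 - rho^2) x 4/(3 + rho).

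- n = 100, p = 0.2, rho = 0.7: c = 0.09/8 = 0.01125; Var(h) = 0.01125 x 0.51 x 4/3.7 = 0.0062; SE = 0.079; E(h) = 0.919 x (-0.05) = -0.046; z = -0.58; rejection about 9%.
- n = 200, p = 0.4, rho = 0.9: c = 0.09/24 = 0.00375; Var(h) = 0.00375 x 0.19 x 4/3.9 = 0.00073; SE = 0.027; E(h) = 0.974 x (-0.05) = -0.049; z = -1.80; rejection about 44%.

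Simulation over these settings gives roughly 10-16% at rho = 0.7 and 17-41% at rho = 0.9, close to the approximation.

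**Step 4: a scale from the documents.** Protocol 2.1.1 reports DAT change of -2.5% and -9.3% in the top and bottom urate quintiles of PRECEPT. On the log scale the difference is ln(0.907/0.975) = -0.072. Using this only as a yardstick for a strong predictor, with 25% or 50% carriers and SD of log change 0.11-0.23, the test rejects in 12-49% of simulated trials with 80 participants, 17-65% with 120 and 27-87% with 200. With delta = 0 it rejects in 5.0%.

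**Step 5: with genotype x visit added.** In simulation the mean of h is about 0 (-0.005 to +0.004) and rejection is 3.5-6.7% across the Step 4 settings. Algebraically Var(h) becomes 2c(1 - rho^2), so the standard error rises by a factor sqrt[(3 + rho)/2], which is 1.36 at rho = 0.7 and 1.40 at 0.9.

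**The case against.** **The SAP governs.** SAP section 1 makes the SAP authoritative on analysis, the SAP lists striatal DAT binding as a secondary efficacy endpoint, and its one genotype model includes genotype x time. But SAP 6.6.7 is written for the primary random-slopes model, and SAP 6.6.3 sends continuous secondary endpoints only to the analyses set out before it. Neither supplies a DAT genotype model. SAP section 1 leaves uncovered ancillary work to ancillary SAPs, which are not in the documents. It therefore stands that the sentence in Protocol 10.5.11 may not be the model finally run.

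**It is shorthand.** This is plausible. One sentence serves gender and genotype, and for gender it is complete. That makes a drafting omission likely, but the text still specifies a biased test for genotype.

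**Software might class-code the three-way term.** It would then take 2 df and absorb genotype x visit. The joint test still rejects in 17-99% of the Step 4 settings, so this helps only if the between-arm contrast is isolated.

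**A prognostic effect on DAT is not shown.** Correct. The progression evidence cited for SNCA and SLC2A9 is clinical, and INPP5K is named for interaction with urate. With no prognostic effect there is no bias.

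**A reader might infer that the substudy would report inosine as harmful in carriers and helpful in non-carriers.** The documents do not support that. The bias for non-carriers is only about p x delta, or 0.01-0.02 log units here. In simulation at correlation 0.9, non-carrier benefit was significant in about 6-16% of runs and carrier harm in 15-22%. SAP 6.6.7 also asks for significantly slower progression within the genotype. Applied to DAT, that would cut false claims of differential benefit to about 3-11%, but Protocol 10.5.11 does not state that rule.

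**Conclusion.** The point holds in a limited form. As written, the genotype test for DAT can attribute to inosine a difference that is purely prognostic. About 86-97% of such an effect goes into the three-way term, depending on scan correlation. A false finding is possible, not certain. How often it would occur depends on substudy size, SD, correlation, carrier share and the genotype's true effect on DAT loss, none of which the documents give. The scan is optional, was added in protocol version 4.0, requires study drug through the one-year visit, and the trial closed early, so numbers may be small. That lowers the false-positive rate but not the bias.

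The scope is one secondary analysis of an optional substudy. The primary DAT comparison and the gender analysis are unaffected, and nothing here bears on the MDS-UPDRS subgroup or genotype models. SAP 6.6.10 gives nominal p-values for secondary endpoints and subgroup analyses, so no multiplicity adjustment is planned that might temper a false finding.

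**What to change.** In the last sentence of Protocol 10.5.11, insert subgroup x visit between the two terms now listed. State that the test of effect modification is the single-df genotype x treatment x post-baseline contrast between arms. Carry both into the SAP or the DAT ancillary SAP, which brings the DAT model into line with Protocol 10.5.3 and SAP 6.6.6 and 6.6.7.

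The cost is one degree of freedom per variant (for a carrier/non-carrier coding) and a less precise interaction estimate, with a standard error about 36-40% larger at correlations of 0.7-0.9 (Step 5). The smaller standard error of the present model comes from assuming that genotype has no prognostic effect on DAT loss. No new data are needed.

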# 11. DATA COLLECTION, SITE MONITORING, AND ADVERSE EXPERIENCE REPORTING

#### 11.1 Records to Be Kept

## 11.1.1 Study File and Site Documents

The Site Investigator should have the following study documents accessible to the Study Monitor during the study.

- Signed Form FDA 1572
- Curriculum vitae for Site Investigator and staff listed on Form FDA 1572
- The signed IRB/IEC form/letter stating IRB/IEC approval of protocol, consent forms and any advertisement notices, documentation of the IRB/IEC composition, and all IRB correspondence including notification/approval of protocol amendments, notification of serious SAEs to the IRB/IEC, and IRB/IEC notification of study termination
- IRB approved consent form (sample) and any advertisement
- Signed protocol (and amendments, if applicable)
- Signed subject consent forms
- Copies of the completed eCRF worksheets (source), supplemental source notes and subject-completed medication logs (Study Drug Record sheets)
- Authorization log (Delegation Log Study Staff and Staff Related Duties) with names, signatures, initials and functional role of all persons completing protocol assessments, providing back-up to the Site Investigator and Coordinator, if applicable, as well as staff entering data into the eRT system.
- Copies of laboratory reports/printouts
- Any source data/records not kept with the subject's hospital/medical records
- Study Drug Dispensing/Return Log and Dose Management Log
- Signed and dated receipt of supplies
- Record of all monitoring visits made by DCC personnel
- Copies of essential site correspondence to and from CCC and DCC
- Investigator's Brochure and IND safety letters, as applicable
- Certificate for Human Subject Protection Program for each individual named on the Authorization log who has direct subject contact
- Copy of professional licensure/registration, as applicable, for each individual named on the Delegation Log, who has direct subject contact ensuring licensure is in the state in which the study will be conducted
- A Note to File indicating the assessments that will be considered source documents
- Any other documentation as required by the CCC or PSG (e.g., Conflict-of-Interest/Financial Disclosure)

The Site Investigator must also retain all printouts/reports of tests/procedures, as specified in the protocol, for each subject. This documentation, together with the subject's hospital/medical records, is the subject's SOURCE DATA for the study.

#### 11.1.2 Maintenance and Retention of Records

US FDA regulations (21 CFR 312.62[c]) require that records and documents pertaining to the conduct of this study and the distribution of investigational drug, including CRFs (if applicable), consent forms,

laboratory test results, and medical inventory records, must be retained by the Site Investigator for two years after marketing application approval. If no application is filed, these records must be kept for two years after the investigation is discontinued and the US FDA and the applicable national and local health authorities are notified. The CCC or their representative will notify the Site Investigators of these events. The Site Investigators should retain all study documents and records until they are notified in writing by the CCC or their representative.

The Site Investigator will be instructed to consult with the CCC before disposal of any study records and to notify the CCC of any change in the location, disposition, or custody of the study files.

#### 11.2 Role of Data Management and Study Monitoring

## 11.2.1 Central Data Management

The Unblinded Biostatistician will be responsible for design of the randomization scheme, creation of analytic databases, and the statistical analysis plan. Data management staff at the DCC will be responsible for all other data collection procedures.

An Internet-accessible Electronic Data Capture (EDC) system for data management will be utilized for this study. This system is protected by 128-bit server certificates and utilizes authenticated, password-protected accounts for each site. The EDC system is designed to ensure timeliness and accuracy of data as well as the prompt reporting of data from the study on an ongoing basis to the study Principal and Co-Investigators. The system is compliant with relevant FDA regulatory requirements per 21 CFR Part 11.

Sites will enter subject information and data into an electronic case report form (eCRF) in the EDC application via computer stations connected remotely through an Internet browser to a central server at the DCC. Authorized study personnel at each site will each be granted access to the electronic data capture tool via provision of a unique password-protected user-ID that will limit access to enter and view data specifically for subjects enrolled at their site.

It is the Site Investigator's responsibility to ensure that entries are proper and complete. During entry of data, error checks will be performed by the EDC that will flag problematic (i.e., missing, out of range, inconsistent) data, allowing for sites to correct the data at that time. Error checks will be implemented in the EDC based upon specifications defined in the data management plan.

Once the data are submitted to the EDC system, they are immediately stored in the central study database located at the DCC and are accessible for review by data management staff. Data review, coding and query processing will be done through interaction with the DCC, site personnel and the Study Monitor. Any changes to the data will be fully captured in an electronic audit trail. The cycle of electronic data entry, review, query identification/resolution, and correction occurs over the course of the study period until all subjects have completed the study. Narrative text of AEs and concomitant medications will be periodically coded using established coding mechanisms.

Upon completion of a subject's visit or the study, sites have the option to print the completed eCRFs depicting the data that were entered. At the conclusion of the study, a PDF (portable document format) file on electronic media depicting eCRFs for each site will be provided by the CCC for record keeping at the site.

Once the Unblinded Biostatistician and the DCC, in conjunction with the Principal Investigator, agree that all queries have been adequately resolved and the database has been deemed "clean", the database will be officially signed off and deemed locked. All permissions to make changes (append, delete, modify or update) the database are removed at this time.

All site personnel will remain blinded as to treatment assignments until the conclusion of the entire study. The treatment assignments are not part of the DCC electronic clinical database. The designated unblinded DCC programmer who oversees the dose adjustment algorithm, the drug packaging staff, and unblinded statistician at the DCC will have access to the treatment assignments, and these individuals will not communicate about treatment-specific results to any other staff involved in the study.

#### 11.2.2 Site Investigator Responsibilities

This study will be conducted under the supervision and direction of the Site Investigator designated by the study Steering Committee as the Site Investigator at the address provided to the CCC.

Clinical supplies will be sent to the address specified to the CCC by the Site Investigator.

The Site Investigator must not conduct the study at any sites other than the one designated by the study Steering Committee.

The protocol, informed consent form, and advertisement notices will be approved by the site's specified institutional IRB.

Each Site Investigator is responsible for providing copies of the protocol and all other information relating to the preclinical and prior clinical experience, which were furnished to him/her, to all study personnel responsible to him/her who participate in this study. The Site Investigator will discuss this information with them to assure that they are adequately informed regarding the study drug and conduct of the study. The Site Investigator must assure that all study staff members are qualified by education, experience and training to perform their specific responsibilities.

## 11.2.3 Case Report Forms

Sites will enter subject information and data into an electronic case report form (eCRF) in the Electronic Data Capture (EDC) application. The eCRFs are used to record study data and are an integral part of the study and subsequent reports. Therefore the eCRFs must be completed for each subject screened or enrolled according to the subject's source data on a per-visit basis. Authorized study personnel will each be granted access to the electronic data capture tool via provision of a unique password-protected user-ID that will limit access to enter and view data specifically for subjects enrolled at their site. **Data should be entered into the EDC system within 3 business days of a subject's visit.** 

Sites will be supplied with a set of source document worksheets that correspond to the electronic case report form (eCRF). The worksheets will serve as source documents and are required to be used to enter data into the eCRFs. Sites will initially enter all data into the subject's medical chart and/or onto source documentation worksheets prior to entering data into the eCRFs via computer stations connected remotely to the central server through an Internet browser.

#### 11.2.4 Electronic Signatures

An electronic signature from the Site Investigator is required on the following eCRFs:

- Signature Form (for each visit)
- Adverse Event Form (at the conclusion of the study)

The data entered from the eCRFs will be securely transmitted to a central database stored on a secure server located at the DCC. Sites must print the completed eCRFs depicting the data that were entered, but have the option to do so upon completion of either a subject's visit or the study.

At the conclusion of the study, the site will be provided with a PDF (portable document format) file on electronic media depicting eCRFs for their site. The PDF file should be printed for each subject participating in the study and filed in the subject's binder.

#### 11.2.5 Primary Source Documents

The Site Investigator must maintain primary source documents supporting significant data for each subject in the subject's medical notes. These documents, which are considered 'source data', should include documentation of:

- Demographic information
- Evidence supporting the diagnosis/condition for which the subject is being studied
- General information supporting the subject's consent to participate in the study
- General history and physical findings
- Hospitalization or Emergency Room records (if applicable)
- Each study visit by date, including any relevant findings/notes by the Site Investigator(s), occurrence (or lack) of adverse events, and changes in medication usage including the date the study drug commenced and completed
- Any additional visits during the study
- Any relevant telephone conversations with the subject regarding the study or possible adverse experiences
- Original, signed informed consent forms for study participation

The Site Investigator must also retain all subject specific printouts/reports of tests/procedures performed as a requirement of the study (e.g., laboratory and ECG reports). Laboratory reports from the central laboratory must be signed and dated by the Site Investigator in a timely fashion following review and filed with the subject's source documents. This documentation, together with the subject's hospital/site medical records, is the subject's 'source data' for the study. During monitoring visits the Study Monitor will need to verify data in the eCRFs against these source data.

